7.0 STATISTICAL SOFTWARE AND COMPUTING HARDWARE

The statistical environment R along with extension packages from the Bioconductor project will be used for carrying out the statistical analyses.^{42,43} When appropriate, bindings with other languages such as Python and C++ will be used. The CALGB Bioinformatics Unit maintains a dedicated 4-way quad-core (16 cores) AMD Opteron 8384 processors with 64GB of RAM, 3TB of usable hard-drive space with RAID 10 redundancy running the Debian GNU/Linux stable AMD64 operating system. The machine can be connected to the CALGB SAN through an iSCSI interface for additional storage. Drs. [name] and [name] also have access to an 8-way Socket F AMD Opteron server with dual core 3.0 Ghz 2222SE processors (total of 16 cores) with 64GB of RAM running Debian GNU/Linux stable AMD64 administered by the Duke Comprehensive Cancer Center Information Science (CCIS). By virtue of their academic affiliations with Department of Biostatistics and Bioinformatics, at the Duke University Medical Center (for whom [name] serves as the chair of the computing committee), will have access to departmental computing resources as well. These include two 8-way Socket F AMD Opteron servers each with dual core 3.0 Ghz 2222SE processors (total of 16 cores) with 64GB of RAM and one 4-way Socket F AMD Opteron server each with dual core 3.0 Ghz 2222SE processors (total of 8 cores) with 32GB of RAM. Additionally, through a collaborative agreement with the Duke HPC group, Drs. [name] and [name] also have access to GPU (graphics processor unit) computing facilities.

APPENDIX III

PHARMACOGENETIC COMPANION STUDIES: CALGB 60905

1.0 OBJECTIVES

- 1.1 To assess the influence of genetic variations in the cyclooxygenase and related pathways on the efficacy of celecoxib as adjuvant therapy for stage III colon cancer
- 1.2 To assess the influence of germline variation in vitamin D pathway genes on disease-free and overall survival in patients with stage III colon cancer.
- 1.3 To investigate the potential association between the AGXT 154C>T polymorphisms and neuropathy in the Caucasian population.
- 1.4 To identify specific SNPs and/or copy number variations that are associated with the prevalence of oxaliplatin-related peripheral neuropathy.
- 1.5 To identify specific SNPs and/or copy number variations that are associated with outcome, severe toxicity, and risk of cancer.

2.0 BACKGROUND

Candidate gene, pathway analyses and whole genome scans are common approaches for the identification of germline polymorphisms that contribute to a given phenotype. A candidate gene approach focusing on drug metabolizing enzymes and drug targets is proposed. In addition, a genome wide single nucleotide polymorphism (SNP) and copy number variant (CNV) scan will be performed to provide more definitive assessment of the genomic contribution to variation in drug effect (see below).

2.1 Genetic variation in COX-2 and related pathways

It is hypothesized that germline polymorphisms in COX related pathway will influence the effect of celecoxib on patient survival. Aspirin and NSAIDs may influence colorectal carcinogenesis, in part, through the inhibition of cyclooxygenase-2 (COX-2; PTSG-2) and COX1 (PTSG-1).^{147,148} COX is the rate-limiting enzyme for the metabolic conversion of arachidonic acid to prostaglandins and related eicosanoids. COX-2 promotes inflammation and cell proliferation and is overexpressed in human colorectal cancer. Polymorphisms in COX-2 (PTGS2) have been associated with the risk of colorectal cancer.^{149,150} In a randomized trial of adjuvant rofecoxib in colorectal cancer patients that was terminated early, 3 COX-2 SNPs (rs10911907, rs11583191, and rs2179555) which lie 5' to the COX2 gene significantly influenced the effect of rofecoxib.¹⁵¹ The effect of rofecoxib was significantly greater in patients with at least one variant allele at each of the three SNP sites (p, interaction = 0.04). Similarly, COX-1 polymorphisms have been linked to the colorectal adenoma risk and appear to modify the influence of aspirin/NSAID use on adenoma risk.¹⁵² 5-lipoxygenase (5-LOX) represents an alternative pathway to COX in arachidonate metabolism. Polymorphism in the promoter region of 5-LOX (ALOX5) has been associated with increased inflammation,^{153,154} levels of C-reactive protein,¹⁵⁵ aspirin-intolerant asthma,¹⁵³ and colorectal cancer.¹⁵⁶ Prostacyclin synthase is a downstream enzyme from COX. A variable number tandem repeat polymorphism in the prostacyclin synthase gene has been associated with altered transcriptional activity and increased risk of hypertension and stroke.¹⁵⁷⁻¹⁵⁹ Thromboxane synthase is an alternative pathway that is downstream from COX. The T(-386)G polymorphism has been associated with an increased risk of myocardial infarction.¹⁶⁰

PPAR γ , a member of the steroid receptor/transcription factor family, is a critical regulator of adipogenesis and a target of the adenomatous polyposis coli (APC) gene.¹⁶¹⁻¹⁶³ PPAR γ may also be a potential target of aspirin and NSAIDs.^{164,165} Animal and clinical studies demonstrate that PPAR γ also has a role in insulin signaling, insulin resistance, development of type 2 diabetes and may function as a tumor suppressor gene.¹⁶³ A common variant in the PPAR γ gene (Pro12Ala) reduces the promoter affinity by approximately 50% and is associated with a reduced risk of type 2 diabetes.¹⁶⁶ Carriers of the PPAR γ 12Ala variant allele were at reduced risk of colorectal neoplasia.^{167,168} Nuclear factor- κ B (NF- κ B) is a ubiquitous transcription factor involved in the regulation of inflammation, apoptosis, and carcinogenesis.^{169,170} Various proinflammatory cytokines (IL-1-beta, IL-8, TNF-alpha) activate NF- κ B, and, in turn, activated NF- κ B promotes colorectal cell proliferation and other inflammatory genes including COX-2.¹⁷¹⁻¹⁷⁵ NF- κ B is constitutively activated in human colorectal cancer, and aspirin-induced suppression of NF- κ B impairs colorectal tumorigenesis. Polymorphisms in NF- κ B have been associated with the increased risk of inflammatory disorders,¹⁷⁶⁻¹⁷⁸ diabetes mellitus,^{179,180} and myeloma.¹⁸¹

The genes involved in celecoxib metabolism will also be examined. CYP2C9 metabolizes both celecoxib and NSAIDs, and variant CYP2C9 genotypes modified the effect of aspirin on adenoma risk in one study.¹⁸² Thus, the efficacy of celecoxib on colon cancer recurrence may be influenced by the metabolism of the agent.

2.2 Germline variations in the vitamin D pathway

The pathway through which vitamin D exerts transcriptional effects is complex. An editorial in the Journal of the National Cancer Institute recommended that future investigations consider the interrelationships of vitamin D and associated genetic polymorphisms within the vitamin D pathway.¹⁸³ In CALGB/SWOG C80702, we will examine the joint effect of vitamin D with polymorphisms in five critical genes in the vitamin D pathway.

The cellular effects of 1-25-dihydroxycholecalciferol [1,25(OH)₂D] – the active metabolite of vitamin D – are principally mediated through the vitamin D receptor (VDR), which regulates the transcription of genes involved in cellular differentiation and inhibition of proliferation.^{184,185} Well-differentiated human colon cancer cell lines have higher VDR expression¹⁰¹ and the antiproliferative effects of vitamin D only occur in cell lines expressing high levels of VDR.¹⁰² Several common polymorphisms (FokI, ApaI, TaqI and BsmI) have been identified in the VDR gene, although functional studies of these polymorphisms have shown contradictory results.¹⁸⁶⁻¹⁹⁴ Moreover, associations between these polymorphisms and the risk of colorectal neoplasia remain inconsistent.¹⁹⁵⁻²⁰² To better define genetic variation in the VDR gene, Nejentsev developed high-resolution SNP, haplotype and linkage disequilibrium (LD) maps of VDR in a multiethnic cohort.²⁰³ A total of 24-26 TagSNPs were required to tag the three haplotype blocks ($r^2 \geq 0.8$). The authors observed that FokI was not in LD with any other common SNP in their study. In addition, ApaI, TaqI and BsmI missed a large fraction of common variation. Therefore, a comprehensive examination of VDR, plasma 25(OH)D, and patient outcome will be performed using these 26 TagSNPs.

Vitamin D binding protein (VDBP, GC) transports vitamin D and its plasma metabolites to target tissues and may also be involved in intracellular metabolism of vitamin D.^{204,205} Two common VDBP polymorphisms (Glu432Asp and Thr436Lys) have been associated with osteoporosis,²⁰³ COPD,²⁰⁴ chronic mucus hypersecretion,²⁰⁸ diabetes,^{204,205} and Grave's disease.²⁰⁹ In contrast, genotyping in 24 unrelated Caucasian individuals of 33 other SNPs with a minor allele frequency >5% revealed little LD across VDBP. Consequently, the investigators will focus on the Glu432Asp and Thr436Lys VDBP polymorphisms.

1- α -hydroxylase (CYP27B1) catalyzes the 1- α -hydroxylation of 25(OH)₂D to 1,25(OH)₂D.²¹⁰ Beyond the proximal renal tubules, the enzyme is present in both normal human colonic mucosa and colorectal adenocarcinomas.²¹⁰⁻²¹⁴ 1- α -hydroxylase polymorphisms have been associated with the risk of Addison's disease, Hashimoto's thyroiditis, Graves' disease, and type 1 diabetes mellitus.^{215,216} We will examine five SNPs with a minor allele frequency >5% (all noncoding) identified in a multiethnic cohort.²¹⁷

Retinoid X receptor (RXR) functions as a heterodimer with the VDR, forming a VDR/RXR complex that regulates transcription of several target genes.^{211,218} Seven SNPs with a minor allele frequency >5% (6 noncoding and one coding, Ser327Ile) will be examined in a multiethnic cohort.²¹⁹

25-hydroxyvitamin D-24-hydroxylase (CYP24A1) initiates degradation of 1,25(OH)₂D and 25(OH)D. CYP24A1 mRNA and protein levels are significantly upregulated in cancers relative to normal tissues, suggesting CYP24A1 may be an oncogene.²²⁰ Polymorphisms in the promoter region of CYP24A1 enhance both basal and vitamin D₃-stimulated promoter activity.²²¹ Six SNPs in the CYP24A1 promoter will be examined.²²²

2.3 AGXT 154C>T polymorphisms and neuropathy

There is increasing evidence which suggests that germline polymorphisms related to anticancer therapeutics metabolism, transport, and resistance correlate with drug response; furthermore, germline polymorphisms related to therapeutic targets and/or therapeutic pathways might also help predict therapeutic outcomes.^{223,224}

This study offers an excellent opportunity to evaluate the role of genetic variants in relevant genes influencing the pharmacology of 5-fluorouracil, oxaliplatin, and celecoxib, which might influence the eventual drug response and/or toxicity of these agents.

The introduction of oxaliplatin to 5-fluorouracil has had a major impact on the treatment of colorectal cancer. However, the efficacy of oxaliplatin-based therapy is often compromised because of the substantial risk for severe toxicities, including neurotoxicity.²²⁵ Oxaliplatin has a direct "pharmacologic" effect on the excitability of sensory neurons and muscle cells that has not previously been described with other platinum agents. Neurotoxicity can result in both acute and chronic debilitation. Moreover, colorectal cancer patients treated with oxaliplatin more often discontinue therapy due to peripheral neuropathy than for tumor progression, potentially compromising patient benefit. Numerous methods to prevent neurotoxicity have so far proven unsuccessful.²²⁵ In order to circumvent this treatment-altering side effect, while taking advantage of the antitumor activities of oxaliplatin, efforts to identify mechanism-based biomarkers are underway.

The neurotoxic effects of oxaliplatin are not seen with exposure to the cytotoxic metabolite, DACH platinum, but rather with the oxalate metabolite. A promising biomarker for risk of oxaliplatin-associated peripheral neuropathy is AGXT, which encodes alanine-glyoxylate aminotransferase. Gamelin et al. proposed that key components of the oxalate synthesis pathway could be associated with platinum-drug neurotoxicity. In a study of 145 patients treated with oxaliplatin, a C to T change in AGXT nucleotide 154 was associated with risk of chronic neurotoxicity.²²⁶ Patients with a C/C genotype (~70% of Caucasians) had a significantly lower incidence of grade 2+ neurotoxicity (~5%) compared to the C/T and T/T patients (~30% of patients, expected incidence of grade 2+ neurotoxicity would be 30%). AGXT is a major enzyme of glyoxylate and oxalate metabolism and 154C>T has a partially reduced activity. These patients seem unable to cope with a brutal inflow of oxalate after oxaliplatin infusion, whose elimination becomes predominantly urinary. Its intracellular concentration increases and it interferes with sodium channels and generates acute neurotoxicity. Our primary hypothesis is

that patients with AGXT 154 C/T or T/T will have a significantly greater incidence of grade 2+ peripheral neuropathy, compared with 154 C/C patients.

Finally, in addition to specific hypothesis testing for the above candidate genes, this study will also provide the framework for hypothesis generation investigations of genotype and/or haplotype in additional candidate genes of putative importance to drug response of the agents being evaluated in this study.

2.4 Genome-wide association studies

Most pharmacogenetic analyses have taken a candidate gene approach that utilizes biological data to guide the selection of drug response genes in a pathway. This approach is limited by our knowledge of the mechanisms underlying the phenotypes. In the case of drug response phenotypes, most candidate gene studies have focused on drug metabolizing enzymes and transporters, thus limiting the chance of discovering causal SNPs not involved in mediating drug levels.^{227,228} In contrast, a genome-wide approach collects SNP data across the entire human genome and has significant power to detect common variants that confer a modest risk for a complex phenotype.²²⁹ Genome-wide studies capitalize on the large number of SNPs (more than 10 million available in dbSNP) that have been localized and validated across the genome, a majority of which have resulted from the HapMap project.²³⁰ This valuable collection of publicly available, validated SNPs has provided the framework for performing genome-wide association studies. Recent technological advancements in genotyping platforms have also enabled the development of genome-wide associations. Searching the whole genome in an association study requires genotyping of anywhere between 10^5 to 10^6 markers across the genome.²³¹⁻²³⁴ Until recently, this approach was fiscally prohibitive and impractical. However, new gene chip platforms from Affymetrix and Illumina have made large-scale genotyping feasible and cost effective. The Illumina Infinium OmniExpress chip that will be used in this study has the capacity to genotype over 555,000 SNPs simultaneously. In addition, there are 4,300 SNPs in regions of copy number variations (CNVs), thus allowing for the detection of CNVs as well. This new capability represents a paradigm shift in the number of genotypes that can be evaluated in any given individual with one genotyping assay and provides a platform for the identification of novel genes involved in the response to and toxicity associated with 5-fluorouracil, oxaliplatin, and celecoxib.

An increasing number of reports of significant findings from genome-wide association studies in cancer are being published. To date, these have all focused on SNPs associated with risk of developing cancer, and include studies in prostate,²³⁵⁻²³⁹ colorectal,²⁴⁰⁻²⁴² lung,²⁴³ and breast cancer.²⁴⁴⁻²⁴⁶ The success of these studies illustrates the power and validity of this approach for identifying genetic causes of disease. The relatively large size of CALGB/SWOG C80702 and robust response and toxicity phenotype data make it an ideal sample set for whole genome analysis. The identification of SNPs that contribute to response and toxicity of the three widely used drugs studied in CALGB/SWOG C80702 will lead to additional studies to understand the mechanism for these associations and to investigate the application of genetic information for the optimization of cancer therapy. The whole genome SNP data will also be useful for biological associations, including those detailed in the correlative science portions of this protocol.

3.0 HYPOTHESES

- 3.1 Genetic variation in COX-2 and related pathway genes will influence the efficacy of adjuvant celecoxib on cancer recurrence.
- 3.2 Germline variation in vitamin D pathway genes (VDR, VDBP, CYP27B1, RXR, CYP24A1) will impact disease-free and overall survival in stage III colon cancer patients. Moreover, polymorphisms in these genes modify the effect of plasma 25(OH)D on patient outcome.
- 3.3 Patients with AGXT 154 C/T or T/T will have a significantly greater incidence of grade 2+ peripheral neuropathy, compared with 154 C/C patients.
- 3.4 Novel SNPs and/or copy number variations will be identified that are associated with the prevalence of oxaliplatin-related peripheral neuropathy as well as DFS and OS.
- 3.5 Genome-wide analyses will elucidate novel genes and pathways associated with risk of recurrence, survival, safety, and efficacy of treatments.
- 3.6 Genome-wide analyses will allow the ascertainment of the genetic basis of risk of sporadic CRC through participation in larger case-control studies of CRC predisposition.

4.0 METHODS

DNA will be available from patients who consented to the pharmacogenomic companion study (CALGB 60905) and provided blood samples (10 mL in EDTA tube). Samples will be banked by the Alliance Biorepository at Ohio State University (OSU). DNA will be isolated and DNA quality will be assessed by UV spectrophotometry and by agarose gel electrophoresis. Phenotypic data will be extracted from research databases by the Alliance statistical group.

4.1 Genetic analysis of candidate genes

For genetic analyses of the candidate genes such as COX-2, vitamin D (VDR, VDBP, CYP27B1, RXR, CYP24A1), and AGXT pathway genes, assays will be performed using previously published methods such as Taqman allelic discrimination or pyrosequencing assays. If more efficient alternative genotyping methods become available in the future, the PET committee will change the genotype approach to optimize resources. Output from the genotyping platforms is entered in a database and forwarded to the Alliance Statistics and Data Center at Duke University where it will be correlated with clinical outcomes.

4.2 Whole-genome genotyping

Illumina's HumanHap550 Genotyping BeadChip enables whole-genome genotyping of over 555,000 single nucleotide polymorphisms (SNPs) loci efficiently and accurately on a single BeadChip. The HumanHap550 BeadChip is powered by the Infinium™ II assay, which uses a single-tube, whole-genome amplification method that does not require PCR and enables intelligent SNP selection using tagSNPs. TagSNPs are loci that can serve as proxies for many other SNPs. The information and power from a larger number of SNPs can be gathered by genotyping only a subset of loci. TagSNPs on the HumanHap550 BeadChip were selected from the recently completed International HapMap Project. The Illumina's HumanHap550 Genotyping BeadChip is one of the platforms that might be used for this study. However, additional platforms, including high-throughput resequencing, might also be used to interrogate the germline genomic variation of patients.

5.0 DATA ANALYSES

5.1 Genetic variation of COX and related pathways

For analyses of germline variation in COX-2 and related pathway genes (objective 1.1), there are several strategies for choosing variants to genotype in specific candidate genes, ranging from selection of a single SNP with proven or potential functional significance, to haplotype- or linkage-disequilibrium tagging approaches. We have chosen the strategy for each gene that we feel can be best justified at this time, taking note of the fact that this is a fast-moving research area. Thus, for most candidate genes, the SNP(s) of proven function, or SNPs with probable function that have been previously associated with the disease, have been chosen. For the most part, the choices are conservative on a gene-by-gene basis, and are the variants that are most likely to interact with the environmental factors proposed, given current knowledge. Although some of the proposed SNPs have been investigated in functional studies, the functional roles of many other SNPs, especially those in the noncoding regions, have been minimally studied.

Candidate SNPs as Effect Modifiers of Celecoxib Efficacy: All polymorphisms will be individually evaluated and categorized as variant or wild type. Baseline characteristics of patients will be compared according to genotype. We will also investigate whether COX-2 and related pathway genotypes modify the relationship between celecoxib use (vs. placebo) and patient outcome. Cox proportional hazards models will be used to calculate multivariable-adjusted HRs and 95% CIs for DFS and OS by celecoxib vs. placebo for each SNP: those with the variant genotype and those with wild type. Tests for statistical interaction will be performed by entering into the model the cross-product term of celecoxib vs. placebo with the genotype as a binary variable. The main effect of each genotype on DFS and OS will also be examined. The main effect analyses will also utilize Cox proportional hazards models to calculate multivariable-adjusted HRs and 95% CIs for DFS and OS by genotype. Multivariate models will be adjusted for confounding variables.

5.2 Germline variations in the vitamin D pathway

For analyses of germline variation in vitamin D pathway genes (objective 1.2), there are several strategies for choosing variants to genotype in specific candidate genes, ranging from selection of a single SNP with proven or potential functional significance, to haplotype- or linkage-disequilibrium tagging approaches. We have chosen the strategy for each gene that we feel can be best justified at this time, taking note of the fact that this is a fast-moving research area. Thus, for most candidate genes, the SNP(s) of proven function, or SNPs with probable function that have been previously associated with the disease have been chosen. For the most part, our choices are conservative on a gene-by-gene basis, and are the variants that are most likely to interact with the environmental factors proposed, given current knowledge. Although some of the proposed SNPs have been investigated in functional studies, the functional roles of many other SNPs, especially those in the noncoding regions, have been minimally studied. In addition, in future analyses, an agnostic approach will be employed and genome-wide association studies will be conducted to identify SNPs that may be associated with plasma 25(OH)D concentrations and patient survival.

Candidate SNPs as Main Effects: All polymorphisms will be individually evaluated and categorized as variant or wild type. Baseline characteristics of patients will be compared according to genotype. The main analyses will utilize Cox proportional hazards models to calculate multivariable-adjusted HRs and 95% CIs for DFS and OS by genotype. Multivariate models will be adjusted for confounding variables. It will be examined whether genetic variation in the vitamin D pathways is associated with vitamin D levels using linear regression. All patients who have available plasma 25(OH)D and genotype data will be included; analyses will be age- and season of blood draw-adjusted. We will also investigate whether vitamin D pathway

CALGB/SWOG C80702

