1.10 Inclusion of women and minorities

This study will be available to all eligible patients, regardless of race, gender, or ethnic origin. There is no information currently available regarding differential effects of oxaliplatin, 5-fluorouracil or celecoxib-based treatment in subsets defined by race, gender, or ethnicity, and there is no reason to expect such differences exist. Therefore, although the planned analysis will look for differences in treatment effect based on racial and gender groupings, the sample size is not increased in order to provide additional power for ethnic subset analyses. In CALGB 89803, 12% (148/1264) of patients were classified as minorities by race and 45% (562/1264) of patients were women. No race or gender differences were observed in CALGB 89803.

Accrual Targets					
Ethnic Category	Sex/Gender				
	Females		Males		Total
Hispanic or Latino	66	+	112	=	178
Not Hispanic or Latino	1034	+	1288	=	2322
Ethnic Category: Total of all subjects	1100 (A1)	+	1400 (B1)	=	2500 (C1)
Racial Category					
American Indian or Alaskan Native	16	+	21	=	37
Asian	39	+	49	=	88
Black or African American	143	+	140	=	283
Native Hawaiian or other Pacific Islander	11	+	14	=	25
White	891	+	1176	=	2067
Racial Category: Total of all subjects	1100 (A2)	+	1400 (B2)	=	2500 (C2)

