The addition of other important clinical and demographic co-variables will be considered. Multivariable models, with molecular, clinical and demographic variables, will be constructed using conditional inference trees and random forests. All secondary and exploratory objectives will be tested at an unadjusted two-sided level of 0.05.

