Population structure that is not appropriately recognized and accommodated can lead to both false positive and false negative results in association studies. We will conduct studies using structure³⁰¹ to estimate ancestry proportions using 10,000 SNPs chosen for having no pairwise LD with unrelated individuals from the HapMap CEU, YRI and CHB+JPT samples used to model the ancestral populations. Substantial previous research has shown this to be a rapid and effective approach to defining historical geographic ancestry. Although self-identified race/ethnicity is usually highly correlated with estimated historical geographic ancestry, there are often a few individuals who appear to be misclassified with self-defined labels, and it is the genetically defined ancestry that is critical to correctly accommodate to ensure robust results from association studies. Each individual will then have estimates of European, African and Asian ancestry. For individuals with high ancestry proportion for a single group (>98%), we will conduct further analyses with eigenstrat³⁰² using all SNPs to determine whether there are additional important sources of variation among individuals leading to detectable stratification by allele frequencies (reflecting, for example, differences in ethnic make-up within individuals of European descent from different U.S. cities from which subjects for the trial were obtained). Primary analyses, described below, will be conducted within groups defined by historical geographic ancestry. Secondary analyses will be conducted using logistic regression with ancestry proportions (and any additional stratification identified using eigenstrat) as covariates.

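### The regression of plasma 25(OH)D on vitamin D pathway SNPs pools all patients and names no ancestry control, although the same appendix controls ancestry elsewhere

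*Combined protocol and SAP*

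**What the plan says.** Appendix III, section 5.2 covers VDR, VDBP, CYP27B1, RXR and CYP24A1. Section 2.2 of that appendix lists the variants: 26 + 2 + 5 + 7 + 6 = 46 SNPs. On coding, section 5.2 says: "All polymorphisms will be individually evaluated and categorized as variant or wild type". It first describes Cox models for DFS and OS by genotype and adds: "Multivariate models will be adjusted for confounding variables". It then turns to the plasma level: "It will be examined whether genetic variation in the vitamin D pathways is associated with vitamin D levels using linear regression". The population and covariates for that regression follow at once: "All patients who have available plasma 25(OH)D and genotype data will be included; analyses will be age- and season of blood draw-adjusted".

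Section 5.2 sets no significance level. The level that applies comes at the end of section 5.3, which counts vitamin D pathway variation among its secondary SNPs: "All secondary and exploratory objectives will be tested at an unadjusted two-sided level of 0.05".

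Ancestry is dealt with in two other places in Appendix III. Section 5.3 limits the AGXT analysis to patients who report themselves as Caucasian. Section 5.4.2 estimates ancestry for the genome-wide work, runs the primary analyses within ancestry groups, uses ancestry proportions as covariates in secondary analyses, and gives the reason: "Population structure that is not appropriately recognized and accommodated can lead to both false positive and false negative results in association studies".

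Protocol section 1.10 states: "This study will be available to all eligible patients, regardless of race, gender, or ethnic origin". Its accrual table targets 2067 White patients of 2500, and 283 in the row "Black or African American".

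**The concern.** A pooled regression of a trait on a genotype is confounded when both vary with ancestry. The SNP coefficient then picks up part of the between-group difference in 25(OH)D, even if the SNP does nothing within any group. Appendix III states this hazard itself and guards against it in two of its analyses, but the guard does not reach this regression. Section 5.2 adjusts for season, which is a determinant of vitamin D exposure, but not for ancestry.

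What is at stake is the credibility of any reported link between a vitamin D pathway SNP and 25(OH)D. As specified, a nominally significant result could not be told apart from population structure.

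**Working it through.** The plan gives no sample size, power or effect size for this regression, so there is no figure of its own to reproduce.

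**Inputs from the documents**
- Share of the minority stratum: w = 283/2500 = 0.1132 (section 1.10).
- n = 1,500, the 60% sample-availability case in Appendix II, section 6.0.
- Binary carrier coding (Appendix III, 5.2) and two-sided 0.05, unadjusted (5.3).

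**Assumptions, not in the documents**
- True SNP effect zero within each ancestry group.
- Allele frequency 0.30 in the majority, so carrier prevalence pA = 1 − 0.70² = 0.51.
- Allele frequency 0.4 to 0.7 in the stratum, so pB = 0.64, 0.75, 0.84 or 0.91.
- Difference in mean 25(OH)D between groups d = 0.3, 0.6 or 0.9 SD (3, 6 or 9 ng/mL if the SD is 10).

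**Formulae** (within-group SD set to 1)
- p̄ = pA + w(pB − pA); Var(G) = p̄(1 − p̄)
- bias β = w(1 − w)(pB − pA)d / Var(G)
- residual variance σ² = 1 + w(1 − w)d² − β²Var(G)
- ncp = β√(n·Var(G)/σ²)
- false-positive rate = Φ(ncp − 1.96) + Φ(−ncp − 1.96)

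**One case in full** (pB = 0.75, d = 0.6)
- p̄ = 0.51 + 0.1132 × 0.24 = 0.5372; Var(G) = 0.2486
- β = 0.1004 × 0.24 × 0.6 / 0.2486 = 0.0581
- σ² = 1 + 0.0361 − 0.0008 = 1.0353
- ncp = 0.0581 × √(1500 × 0.2486 / 1.0353) = 1.10
- rate = Φ(−0.86) + Φ(−3.06) ≈ 0.20

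**All cases, false-positive rate at nominal 5%**

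| 25(OH)D difference | allele freq. 0.4 | 0.5 | 0.6 | 0.7 |
|---|---|---|---|---|
| 0.3 SD | 6% | 9% | 12% | 15% |
| 0.6 SD | 9% | 20% | 33% | 45% |
| 0.9 SD | 14% | 37% | 61% | 77% |

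Simulation in the same settings (2,000 datasets each) gave 6–16%, 10–45% and 16–78% for the three rows. A smaller simulation (1,000 datasets each) put the lowest cell at 5%.

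**A second parameterisation.** With 40% carriers in the majority, d = 0.5 and n = 1,500, carrier gaps of 10, 20 and 30 points give 6.8%, 12.2% and 21.4% by formula. Simulated regressions that included age and season (3,000 runs each) gave 6.6%, 11.2% and 20.6%.

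**Controls.** If either the carrier gap or the 25(OH)D difference is zero, the rate stays at 5%. With an ancestry term in the model, the simulated rate was 4.4% to 5.4% in the second parameterisation and 4% to 6% in the first.

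**The case against.** The strongest reply is that the plan already covers the point. Section 5.2 promises adjustment for confounders, section 5.3 says further demographic variables will be considered, and 5.4.2 handles ancestry. None of these reaches the regression. The confounder sentence follows the DFS and OS models and names no variable, and the regression then gets its own covariate list. Section 5.3 only undertakes to consider covariates, and reading its Caucasian restriction across would contradict the all-patients population in 5.2. Section 5.4.2 governs the genome-wide work; a genome-wide analysis of 25(OH)D is left to the future. It is true that 5.2 does not say age and season are the *only* covariates. They are the only ones named.

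A second reply also stands: the size rests on assumed values, and inflation could be negligible.

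A reader might infer more than the documents support:
- **That false SNP associations carry into the genotype-by-25(OH)D outcome models.** Those Cox models are fitted for each SNP from measured 25(OH)D and genotype. The regression neither selects SNPs for them nor supplies an input.
- **That the DFS and OS models ignore ancestry.** Sections 5.1 and 5.2 both promise adjustment for confounders. They leave all of them unnamed, which is a gap in detail, not an omission of ancestry in particular.
- **That the celecoxib-by-SNP tests in 5.1 are compromised.** Celecoxib is randomised, so ancestry biases that test only if it modifies the celecoxib effect, and section 1.10 sees no reason to expect this. A simulation with a 40-point carrier gap and an assumed ancestry DFS hazard ratio of 1.5 rejected 6.0% of the time (500 runs, standard error about 1 point).

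**Conclusion.** The point holds for one analysis: the regression of 25(OH)D on candidate genotype in Appendix III, 5.2. As written it pools all patients, names age and season of blood draw as its covariates, and omits a control that the same appendix treats as necessary elsewhere.

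The omission is plain from the text; its consequence is conditional. Inflation needs both a carrier-frequency difference and a 25(OH)D difference across ancestry groups, and the documents quantify neither. Over the assumed range the false-positive rate runs from about 5% to about 77%. It is therefore not shown that any particular SNP will be falsely reported.

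The regression is a secondary companion analysis. The primary DFS comparison of celecoxib with placebo is untouched. The matter merits correction because the remedy is specific and nearly free.

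**What to change.** In Appendix III, 5.2, state that the 25(OH)D regression will be run within the ancestry groups defined in 5.4.2, or with the ancestry proportions or principal components from that section as added covariates. Where array data are missing, use the self-reported race already collected on the case report form. This fallback is needed because section 4.1 allows candidate SNPs to be typed by single-SNP assays, which would not yield ancestry estimates.

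For the SNP main-effect models for DFS and OS in 5.1 and 5.2, name ancestry among the confounders already promised.

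The change is not offered as a complete remedy for the genotype-by-25(OH)D interaction tests: a main-effect ancestry covariate alone would not fully protect a product term.

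The cost is a sentence or two of text and a few degrees of freedom, with no new sample, visit or form.
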